5.7 Safety and tolerability evaluation

5.7.1 Adverse events

A treatment emergent adverse event (TEAE) is defined as an adverse event (AE) that appears during or after study treatment and was absent before.

An AE overview table will be created displaying the number and percentage of subjects experiencing a treatment-emergent adverse event (TEAE) and the number of TEAEs for: any TEAE, any mild/moderate/severe TEAE, any related/unrelated TEAE, any serious AE, and any TEAE leading to study discontinuation.

Furthermore, all TEAEs will be tabulated by System Organ Class (SOC) and Preferred Terms (PTs) within each SOC according to the MedDRA terminology list, using frequency counts (number of subjects with at least one event, and number of events) and percentage of subjects with the event.

TEAEs will also be tabulated by severity (mild/moderate/severe) and by relationship to study medication (related/unrelated). Similar tables will be created for TEAEs leading to premature discontinuation, SAEs and deaths, if applicable. These summary tables will be presented by decreasing frequency of occurrence based on SOC and PT.

In addition, similar TEAE tables (overall, by severity and by relationship, premature discontinuation, SAEs, and deaths) by SOC and PT will be presented per treatment cycle, and frequencies and percentages will be determined for the active treatment cycle and the washout cycle. The treatment cycle is the period between start of first treatment at Visit 2 and 24 hours after last dose at Visit 4. The washout cycle starts 24 hours after last dose at Visit 4 until and including Visit 6.

The summary tables will be accompanied by individual subject listings of *all* AEs including information on AE number, actual AE description, date/time of start and end of AE (or ongoing), PT (MedDRA), SOC (MedDRA), severity, relationship, pre-dose (yes/no), seriousness, action taken, outcome and other information collected in the CRF for adverse events. Pre-dose AEs are not considered to be treatment-emergent, except in case of worsening during/after study treatment (to be collected as separate AE in the database). AEs

starting prior to administration of the study drug will only be listed. In this listing, a clear distinction will be made between prior and treatment emergent events.

To address the study delays due to Covid-19 in reference to AE occurrences, AE incidence rates will also be determined per study cycle (treatment cycle and washout cycle). Incidence rate of adverse events is defined as the number of adverse event cases per patient-year(s). The calculation of the incidence rate is the number of cases (i.e. patient with an AE) divided by the sum of the follow-up time of all patient at risk (which will be all subjects receiving treatment). This calculation is accomplished as follows:

- Denominator: $\sum p_i \times t_i$, where p_i = patient i and t_i = treatment duration of patient i in years (total # days divided by 365.25), where treatment duration is determined based on first and last (dose) date.
- Numerator: the total number of cases (note: a single patient can be counted more than once if the AE occurs on separate occasions)
- Incidence rate = numerator/denominator

The use of this measure implies the assumption that the incidence rate is constant over different periods of time. Since the calculation is done per cycle, the denominator (patient-years) is also determined per cycle, based on the patients available within that cycle.

Separate listings will be created for SAEs and deaths, if applicable. The SAF population is used for the AE presentations.

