4.3 Patient Withdrawal

Patients may withdraw from the study at any time at their own request without stating the reason(s) for withdrawal. If a patient withdraws early from the study after start of treatment an early termination (ET) visit should be arranged, preferably 7-14 days after the last dose of study drug.

"Non-naïve" patients (including "naïve" patients reclassified as "non-naïve") will be withdrawn from the study if their urine sample from **Visit 1** (Baseline 1) detects levels of N-Acetyl-D-Leucine above the permitted threshold.

The treating physician may decide that a patient should be withdrawn from the study or from the study drug. Reasons for withdrawal from the study or the study drug may include, but are not limited to, the following:

- Development of any adverse event (AE), serious AE (SAE), laboratory abnormality, condition, intercurrent illness, injury, medical condition, or use of a medication that is likely to interfere with patient safety, the overall assessment, or the study procedures, such that continued participation in the study would not be in the best interest of the patient.
- Consent withdrawal.
- The patient becomes pregnant or plans to become pregnant.
- Significant patient noncompliance, defined as an unwillingness to complete the procedures defined in the schedule of events.
- Patient lost to follow-up (i.e., staff unable to contact patient after several attempts).
- Investigator, Medical Monitor, and/or Sponsor decision for any other reason not listed above that may invalidate the results of the study or jeopardizes the health and/or safety of a patient
- Complications related to pandemics such as COVID-19.

Patients who discontinue study drug prior to completing the full treatment period, should be asked to complete the remaining study visits as far as possible and complete safety assessments at a minimum. If unwilling to complete the remaining study visits, regardless of the reason for withdrawal, best efforts should be made to have the patient take part in early termination (ET) procedures, preferably 7-14 days weeks following the last dose of the study drug, unless the

patient is lost to follow-up or has withdrawn his/her consent to further study participation. Due to COVID-19, the ET visit may need to be postponed or conducted remotely, after discussion with the PI and the Sponsor.

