5.2 Administration

All patients are to receive N-Acetyl-L-Leucine (IB1001) in this single-arm study; there will be no comparator or placebo.

During the treatment period of this study, the dosing of the study drug is as follows:

- Patients aged ≥13 years in Europe and aged ≥18 years in the United States will take 4 g
 per day: 2 g in the morning, 1 g in the afternoon, and 1 g in the evening.
- Patients aged 6-12 years weighing 15 to <25 kg will take 2 g per day: 1 g in the morning and 1 g in the evening.
- Patients aged 6-12 years weighing 25 to <35 kg will take 3 g per day: 1 g in the morning, 1 g in the afternoon, and 1 g in the evening.
- Patients aged 6-12 years weighing ≥35 kg will take 4 g per day: 2 g in the morning, 1g in the afternoon and 1 g in the evening (as per patients aged ≥13).

The planned maximum dosage for patients \geq 13 years, or aged 6-12 weighing \geq 35 kg is 4 g per day for 42 days (+7 days).

Patients aged 6 to 12 years and <35 kg will receive 2 g or 3 g per day for 42 days (+7 days), in accordance with their body weight (see above).

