5.3 Modification of Dose Schedule

On visit days, patients should keep to their usual dosing schedule.

If a patient misses a dose of study drug, the patient should wait and take the next dose according to the treatment schedule.

Compliance will be assessed upon a review of the inventory of IB1001 bottles returned from patients.

The patient's total daily dose may be reduced by up to one-half of their assigned dose at the discretion of the investigator.

In the event a patient turns 13 years old, or a patient aged 6-12 years old changes weight category over the course of the study, their daily dose will not change from the initial dosing regimen prescribed at Visit 2, the start of IMP.

Study drug will be taken during the 42-day (+7 day) treatment period. After the 42-day (+7 day) treatment period, patients will enter a 42-day (+7 day) washout period, which includes efficacy and safety assessments.

If Visit 4 is postponed due to COVID-19, patients who remain in the study must be dosed through the postponed Visit 4. The study drug will therefore be taken longer than the planned 42 days (+7 days). Based on the known risk/benefit profile of IB1001, the Sponsor's Medical Expert, Medical Monitor, the DSMB, and each Principal Investigator have determined that postponing Visit 4 will not compromise the safety of the patient, nor would continuing the patient on IMP until the postponed Visit 4.

Note: at the time of the initial COVID-19 outbreak, the Extension Phase (providing patients with further access to treatment for one-year) had been accepted by all applicable Competent Authorities (CA)/ Institutional Review Boards (IRB)/ Research Ethics Committees (REC) where the trial is being conducted, supporting the continued dosing of patients until the postponed in person Visit 4.

See Section 5.9 for information on the treatment of overdose.

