5.8.2 Dosing and treatment compliance

Relevant dosing information (first dosing date, last dosing date), scheduled and actual dosing dates/times and treatment compliance information will be determined and listed for each patient. Summary statistics for the number of N-Acetyl-L-Leucine doses taken during the

Parent study phase, based on bottles/sachets of dispensed and returned unused bottle/sachets counts, will be calculated. Compliance is defined as 100% * (total number of IB1001 bottles and/ or sachets dispensed – total number of IB1001 unused bottles and/ or sachets returned), divided by the number of bottles which should have been used. Note that the number of bottles and/ or sachets the patients should have used depends on the dosage they should take (see Section 2.3 for reference) and the duration of the treatment period. Considering the fact that the patient's total daily dose may be reduced by up to half of their assigned dose at the discretion of the investigator, the actual dose will be used to determine the correct compliance calculation, if collected in the eCRF. The proportion of patients who take at least 80% of the prescribed medication will also be shown. Total dosing period is defined as the duration (in days) between first dose date and last dose date.

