11.4 Listings

Following ICH E3 guidelines, all listings mentioned here will be presented in Section 16.2 of the CSR, and listings will be prepared in the order and with section number as stated.

Individual listings will be prepared of the data collected in the database, following SDTM data format. No combining of data other than mentioned in this paragraph will be performed. The key variables in the listings (except for a few displaying screening data) will be patient number, and age/weight/dosing group. If applicable, visit number will be listed additionally. Furthermore, a listing containing study visit dates will be presented.

Listing number	Contents of listing
16.2.1 Discontinued patients	
16.2.1.1	Inclusion/exclusion criteria – deviations
16.2.1.2	Patient disposition
16.2.2 Protocol deviations	
16.2.2	Protocol deviations
16.2.3 Demographic and baseline data	
16.2.3.1	Demographics

16.2.3.2	Baseline characteristics
16.2.3.3	Medical history
16.2.3.4	NPC specific history
16.2.4 Compliance and/or treatment data	
16.2.4.1	Drug administration
16.2.4.2	Drug accountability
16.2.4.3	Study visits
16.2.5 Individual efficacy response data	
16.2.5.1	Individual CI-S and CI-CS scores
16.2.5.2	Individual scores on ataxia and functioning - SARA test
16.2.5.3	Individual scores on ataxia and functioning - SCAFI test
16.2.5.4	Individual health related quality of life – EQ-5D-5L, EQ-5D-Y and the respective EQ-VAS
16.2.5.5	Individual overall neurological status – mDRS test
16.2.5.6	Individual global impression scores – CGI-S (treating physician, caregiver, and patient)
16.2.5.7	Individual change in global impression scores – CGI-C (treating physician, caregiver, and patient)
16.2.6 Adverse event listings	
16.2.6.1	Adverse events
16.2.6.2	AEs leading to discontinuation from the study
16.2.6.3	Vital signs
16.2.6.4	ECG
16.2.6.5	Prior and concomitant medication and therapies
16.2.7 Listing of individual laboratory measurements by patient	
16.2.7.1	Laboratory safety data – haematology
16.2.7.2	Laboratory safety data – clinical chemistry
16.2.7.3	Laboratory safety/pregnancy data – urinalysis
16.2.7.4	Listing of urine test for N-Acetyl-D-Leucine

16.2.7.5	Listing of PK concentration data
16.2.7.6	General comments

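### The safety tables do not show which adverse events led to stopping, reducing or interrupting the drug, and the compliance percentage conceals dose reductions

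*SAP*

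**What the plan says.** **Adverse events.** The overview table in SAP 5.7.1 ends with "any related/unrelated TEAE, any serious AE, and any TEAE leading to study discontinuation". For the tables by system organ class and preferred term, the same section says: "Similar tables will be created for TEAEs leading to premature discontinuation, SAEs and deaths, if applicable". That phrase carries into Tables 14.3.1.5 and 14.3.1.9 (Parent Study) and 14.3.1.14 and 14.3.1.18 (Extension Phase) and is not defined anywhere. The matching Parent Study listing, 16.2.6.2, is titled "AEs leading to discontinuation from the study", and Extension Listing 16.2.6.7 has the same title. The action taken for each event is named only as a field in the per-patient listing.

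**Stopping and reducing the drug.** Protocol 4.3 allows withdrawal from the study or from the drug alone and says: "Patients who discontinue study drug prior to completing the full treatment period, should be asked to complete the remaining study visits as far as possible". Protocol 5.3 says: "The patient's total daily dose may be reduced by up to one-half of their assigned dose at the discretion of the investigator". Section 5.3.1 of the Extension Phase protocol repeats the reduction rule.

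**Disposition.** Protocol 8.1.1, in both phases, undertakes to present how many patients discontinue treatment and their main reason. SAP 5.5.4 and 6.5.4 summarise reasons for non-completion and do not name treatment discontinuation.

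**Compliance.** SAP 5.8.2 divides bottles dispensed less unused bottles returned by the bottles that should have been used. Where a dose has been reduced, "the actual dose will be used to determine the correct compliance calculation, if collected in the eCRF". It adds: "The proportion of patients who take at least 80% of the prescribed medication will also be shown". SAP 6.7 and 6.8 carry the safety and compliance rules into the Extension Phase.

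**The concern.** Safety and tolerability at 4 g/day, or at the weight-tiered dose, is a secondary objective of both phases. The usual summary evidence is how many patients stopped, interrupted or reduced the drug because of an adverse event. The plan specifies no such count. Its one explicit discontinuation row measures leaving the study, which the protocol tries to prevent in patients who stop the drug. The better sites follow that instruction, the fewer drug stops the row will contain.

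The compliance percentage might be expected to show that patients did not stay on their assigned dose. For reductions it cannot, because its denominator falls with the dose. A report could therefore show few or no discontinuations due to adverse events and high compliance even though some patients had stopped the drug and others were on half dose. A reader would have to go through the listings patient by patient to find this.

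**Working it through.** The plan states no figure on this point, so there is nothing to reproduce. The check compares the passages and then applies the SAP's compliance formula.

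**1. Who is counted as discontinuing**

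- Protocol 3.3: a patient completes the Parent Study by completing all its phases, including Visit 6.
- Protocol 4.3: a patient who stops the drug is asked to attend the remaining visits. Protocol 6.2.1 also recognises patients who are off treatment but still on study.
- SAP 5.7.1: the overview row counts events leading to discontinuation of the study.

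A patient who stops the drug for an adverse event and attends through Visit 6 is a completer and is not in the row. A patient whose dose is reduced or interrupted is not in it either, and no other table is specified for these actions. SAP section 7, which lists departures from the protocol, does not mention dropping the Protocol 8.1.1 count of treatment discontinuations.

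**2. Compliance after a dose reduction**

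Inputs:
- assigned dose 4 g/day (Protocol 5.2), in 1000 mg bottles (Protocol 5.1), so 4 bottles a day
- planned treatment of 42 days (Protocol 3.1.2.2), ignoring the +7-day window
- dose halved, the largest reduction allowed (Protocol 5.3)
- assumed: every prescribed dose is taken, and the reduction comes after *d* full-dose days

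Formulas:
- bottles assigned = 4 × 42 = 168
- bottles used = 4*d* + 2(42 − *d*) = 84 + 2*d*
- SAP rule, actual dose: (84 + 2*d*)/(84 + 2*d*) = 100% for every *d*
- assigned dose: (84 + 2*d*)/168 = 50% + *d*/84

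| Full-dose days before halving | Bottles used | Compliance, actual dose | Percent of assigned dose |
|---|---|---|---|
| 0 | 84 | 100% | 50.0% |
| 7 | 98 | 100% | 58.3% |
| 14 | 112 | 100% | 66.7% |
| 21 | 126 | 100% | 75.0% |
| 25 | 134 | 100% | 79.8% |
| 26 | 136 | 100% | 81.0% |
| 28 | 140 | 100% | 83.3% |

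The assigned-dose figure is below 80% when *d* < 0.30 × 84 = 25.2, that is, after 25 or fewer full-dose days. The percentages are the same for the 3 g and 2 g tiers because the assigned dose cancels.

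**3. Compliance after an early stop**

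SAP 5.8.2 bases the denominator on the dosage and the length of the treatment period, and defines the first-to-last-dose interval separately. Read that way, a patient who stops after 7 days scores 28/168 = 16.7% and fails the 80% criterion. Masking in the compliance figure therefore applies to reductions and not to stops.

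**4. Whether the doses-taken summary fills the gap**

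SAP 5.8.2 also summarises the number of doses taken, and there a halved 4 g patient does differ from a full-dose one (84 against 168 bottles). The summary is not specified by dose tier, however. A fully dosed 2 g patient also uses 2 × 42 = 84 bottles, so the total alone does not identify a reduction.

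**The case against.** The strongest reply is that little is hidden. All treatment-emergent events are tabulated by system organ class and preferred term, by severity, by relationship and by treatment cycle, with incidence rates per cycle. Doses taken are summarised. Action taken, drug administration and accountability are listed for each patient, and with about 39 patients the counts can be recovered by hand. Premature discontinuation is undefined and could include stopping the drug. Measuring adherence against the dose actually prescribed is a legitimate definition, and the actual-dose rule applies only if that dose is in the eCRF. Protocol 5.3 leaves reduction to the investigator's discretion and does not tie it to adverse events.

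Much of this stands, and it rules out two stronger readings. A reader might infer that poor tolerability vanishes from every summary table. It does not, because the events themselves remain in the general tables. A reader might also infer that patients who stop the drug will score as fully compliant. The SAP does not support that, because the adjustment is written for reductions and an early stop lowers the score.

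The reply does not restore the link between event and action on the drug. The general tables show that an event occurred, not that the drug was stopped or reduced because of it. The discontinuation wording that does name its object (the overview row and the two listings) refers to the study. A count that must be rebuilt by hand from listings is not a planned summary of a secondary objective.

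**Conclusion.** The point holds as a reporting gap. The plan specifies no count of events leading to drug withdrawal, reduction or interruption. It leaves premature discontinuation undefined in four tables and does not carry out the Protocol 8.1.1 commitment on treatment discontinuations. Its compliance percentage also cannot tell a full-dose patient from a half-dose one.

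On size, a patient halved from day 1 scores 100% compliance on 50% of the assigned dose. Every halving after 25 or fewer full-dose days is classed as at least 80% compliant while below 80% of the assigned dose. These figures assume full adherence, a 42-day course, a halved dose and an actual dose recorded in the eCRF. Each patient missing from the overview row is 1/39 = 2.6 percentage points of planned enrolment, although the adverse event tables will use the safety set.

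The documents do not say how many patients will be affected and give no basis for an expected rate. Protocol 3.1.2.5 describes very good tolerability to date. The efficacy analyses are not touched.

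**What to change.** 1. In SAP 5.7.1 and 6.7, keep the study-discontinuation row. Add rows for treatment-emergent events leading to permanent discontinuation of study drug (whether or not the patient stays on study), to dose reduction and to interruption. Take these from the action-taken field as far as its response options permit; the documents do not show those options, so check them first.
2. Define premature discontinuation in Tables 14.3.1.5, 14.3.1.9, 14.3.1.14 and 14.3.1.18 as discontinuation of study drug.
3. In SAP 5.5.4 and 6.5.4, add the number of patients discontinuing treatment, with the main reason, as Protocol 8.1.1 promises for both phases.
4. In SAP 5.8.2 and 6.8, report percent of assigned dose taken beside actual-dose compliance, with the number of patients whose dose was reduced.

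The cost is SAP wording and a few table rows. No treatment, visit or endpoint changes. The downside is that reported tolerability may look slightly less favourable.

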3.1.2.2 Treatment Period

From Visit 2 onward, all visits will be the same for all patients regardless of whether they were considered to be "naïve" or "non-naïve" at the time of screening.

During the treatment period, all patients will receive N-Acetyl-L-Leucine for 42 days (+7 days). **Visit 3** (Treatment 1) will occur at Day 28 (+7 days) of the treatment period and **Visit 4** (Treatment 2) will occur after the full 42 days (+7 days) of treatment.

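### The per-cycle AE rate in SAP 5.7.1 takes time at risk from dosing dates, which cannot measure washout, and separately defines its numerator in two ways

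*SAP*

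**What the plan says.** SAP 5.7.1 adds AE incidence rates per patient-year, by study cycle, because COVID-19 delays change how long patients are observed.

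**Cycle bounds.** These are given earlier in the same section. Treatment is counted from the first intake at Visit 2 to one day past the final intake. For the period off drug, the section says: "The washout cycle starts 24 hours after last dose at Visit 4 until and including Visit 6".

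**Denominator.** The section describes it in three ways:
- In the opening definition, as the follow-up time of everyone at risk.
- In the formula, as the sum over patients of treatment duration in years, "where treatment duration is determined based on first and last (dose) date".
- In a closing remark: "the denominator (patient-years) is also determined per cycle, based on the patients available within that cycle".

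**Numerator.** The opening definition reads "number of cases (i.e. patient with an AE) divided by the sum of the follow-up time of all patient at risk". The calculation step then asks for the total number of cases and notes that "a single patient can be counted more than once if the AE occurs on separate occasions".

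**Extension Phase.** SAP 6.7 says its safety evaluation is similar to that of the Parent Study. It defines a washout cycle running from 24 hours after the last dose at Visit 9 through Visit 10.

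**The concern.** There are two separate defects.

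1. **Time at risk.** The washout cycle begins after dosing has ended, so first and last dose dates cannot give its length. A programmer who applies the formula as printed would divide washout events by treatment time. The error then depends on how far the two lengths differ. They differ most in patients with a postponed Visit 4 or Visit 6, who are the reason these rates were added.

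2. **Numerator.** Patients with at least one event and all events with repeats give different rates. This holds at any cycle length and has nothing to do with the first defect.

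The trial has one arm, so the comparison of treatment with washout is the main on-drug versus off-drug view of safety after dosing starts. A distorted washout rate would change that comparison, in either direction. If the definition is left open, it could also be settled after the counts are known.

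**Working it through.** The documents report no AE incidence rate, so there is no figure of the plan's to reproduce.

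**Inputs from the documents**
- Planned treatment length T: 42 days (+7) (Protocol 3.1.2.2).
- Planned washout length W: 42 days (+7) (Protocol 3.1.2.3).
- Visits 4 and 6 may be postponed, and dosing continues to a postponed Visit 4 (Protocol 3.1.2.5.2 and 5.3). No upper limit on the delay was found.
- Extension: treatment 365 days (±14), washout 42 days (+14) (Protocol Appendix 6, 3.1.2.2 and 3.1.2.3).
- About 39 patients enrolled (Protocol 3.1.3).

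**Assumed, because the documents give no values**
- 20 washout events in 12 patients, with a range of 12 to 30 events.
- Delayed lengths of 84 and 126 days, marked * below.

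**Defect 1: time at risk**

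For E washout events:
- Literal reading: rate = E / (ΣT / 365.25).
- Cycle reading: rate = E / (ΣW / 365.25).
- Literal over cycle = ΣW / ΣT, which is W/T when all patients have the same lengths. E and the number of patients cancel.

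With 39 patients and 42 days, person-time is 39 × 42 / 365.25 = 4.485 patient-years, and 20 / 4.485 = 4.46 per patient-year. The other rows follow in the same way:

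| T (days) | W (days) | Literal rate | Cycle rate | Factor W/T |
|---|---|---|---|---|
| 42 | 42 | 4.46 | 4.46 | 1.00 |
| 49 | 42 | 3.82 | 4.46 | 0.86 |
| 42 | 49 | 4.46 | 3.82 | 1.17 |
| 84* | 42 | 2.23 | 4.46 | 0.50 |
| 126* | 42 | 1.49 | 4.46 | 0.33 |
| 42 | 84* | 4.46 | 2.23 | 2.00 |

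For the Extension, the factor is 42 / 365 = 0.12, or 56 / 365 = 0.15 at the end of the washout window. No delay is needed to produce it.

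The factors for delayed visits apply if every patient is delayed alike. In a mixed group the factor is total washout time over total treatment time, so undelayed 42/42 patients pull it toward 1.

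There is a smaller mismatch in the treatment cycle, which runs 24 hours past the last dose. At 42 days of dosing, 43 / 42 = 1.024, so a denominator of dosing days alone makes the treatment rate about 2.4% too high.

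**Defect 2: numerator**

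Over the same 4.485 patient-years, with 12 affected patients:
- Patients: 12 / 4.485 = 2.68 per patient-year.
- 20 events: 20 / 4.485 = 4.46, a factor of 20 / 12 = 1.67.
- 30 events: 30 / 4.485 = 6.69, a factor of 30 / 12 = 2.5.
- 12 events, one each: 2.68, a factor of 1.00.

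The factor is events per affected patient. T and W do not enter it.

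**The case against.** The strongest reply is that the section as a whole means cycle time. The opening definition speaks of follow-up time. The word dose stands in brackets, so the dates can be read as the first and last dates of the cycle. The closing remark makes patient-years, a quantity of time, specific to each cycle, and the bounds are printed earlier in 5.7.1. On that reading, unequal lengths cause no error.

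This stands as the likely intention. It does not repair the formula:
- The closing remark gives no dates. Its second half can be taken to change only which patients are summed.
- Follow-up time does not clearly mean cycle time. In SAP 5.5.4 it runs from first dose to the end of the parent phase.
- SAP 5.8.2 defines a total dosing period from first to last dose, a variable that the printed formula matches directly.
- The table list in SAP 11.3 names no incidence-rate table that would settle the matter.

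On the numerator, the reply is that the calculation step governs and describes an event rate, so the earlier parenthesis is loose wording. That is a fair reading, and the fix adopts it. The text still contradicts itself until the parenthesis goes.

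The effect is also limited. The rates are supplementary and descriptive. TEAE counts and percentages by cycle are planned alongside, and AE, visit and dosing dates are listed, so the rates could be recomputed. SAP Section 8 places COVID-19-specific items in a separate Addendum 1, which is not among the documents reviewed and might clarify the dates.

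A reader might go further and infer that washout rates will be wrong whenever the cycles differ in length, and that the double numerator is part of the same error. The documents do not support either inference. The first holds only if the formula is applied literally against the closing remark. The second fails because the numerator problem is unrelated to length.

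**Conclusion.** The point holds as two separate corrections to one paragraph.

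The only explicit definition of time at risk cannot measure washout, and the sentence that hints at the right one supplies no dates. The size of this defect is conditional on the literal reading. It is nil at the planned lengths and modest within the visit windows. It becomes material only with postponed visits, whose lengths here are assumed, or in the Extension Phase. Whether the Extension uses the rate at all is unclear: SAP 6.7 says only that the evaluation is similar, and SAP Section 8 says that no COVID-19-specific measures apply there.

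The numerator contradiction is on the page and needs no assumption. Its size depends on how often events recur in a patient, which the documents do not indicate.

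No hypothesis test, sample size or stated decision rule uses these rates. The correction should be made before analysis, but efficacy conclusions do not depend on it.

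**What to change.** In SAP 5.7.1:

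1. Replace the dose-date definition with cycle time per patient. Treatment: first dose to 24 hours after last dose. Washout: 24 hours after last dose to Visit 6, or to withdrawal or last contact if earlier.
2. Delete the parenthesis that equates a case with a patient who has an AE. Name the measure an event rate: all events in the cycle divided by total cycle time.
3. If a patient-based rate is also wanted, give it separately, counting first events and ending each patient's time at the first event.
4. In SAP 6.7, state whether the rate is produced for the Extension Phase. If it is, use the cycle bounds listed there.

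The cost is a few lines of SAP text and the matching programming specification. No new data are needed: SAP 5.8.1 and 5.8.2 already list visit and dosing dates, and the cycle bounds are already written.
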